4 STUDY DRUG

Study drug includes both Investigational [Medicinal] Product (IP/IMP) and Non-investigational [Medicinal] Product (Non-IP/Non-IMP) and can consist of the following, listed in Table 4-1:

Table 4-1: Study Drugs for CA209742

Product Description/Class and Dosage Form	Potency	Primary Packaging (Volume)/Label Type	Secondary Packaging (Qty)/Label Type	Packaging/Appearance	Storage Conditions (per label)
Nivolumab Solution for Injection ^a	100 mg (10 mg/mL) or 40 mg (10 mg/mL)	10 mL per vial Or 4 mL vial/Open label	5 or 10 vials per carton/ Open-label Or 240 mg kits (2-100 mg vials and 1-40 mg vial)	Clear to slightly opalescent, colorless to pale yellow liquid. Light (few) particulates may be present.	2° to 8 °C. Protect from light and freezing
Ipilimumab	200 mg (5 mg/mL)	40 mL per vial/Open-label	4 vials per carton/Open-label	Clear to slightly opalescent, colorless to pale yellow liquid. Light (few) particulates may be present.	2° to 8 °C. Protect from light and freezing
BMS-986214 Solution for Injection (Nivolumab/Ipilimumab FRC)	40 mg Nivolumab/ 120 mg Ipilimumab	26 mL vial/Open-label	6 vials per carton/Open-label	Clear to opalescent, colorless to pale yellow liquid. Light (few) particulates may be present	2° to 8 °C. Protect from light and freezing

^a Nivolumab is labeled as BMS-936558-01 Solution for Injection

The fixed ratio combination drug product is formulated by combining the nivolumab drug substance and ipilimumab drug substance at a nivolumab/Ipilimumab protein-mass ratio of 1 to 3. The composition and manufacturing process of these 2 drug substances are the same as those used for the nivolumab and ipilimumab commercial drug products.

The Sponsor has conducted quality testing to demonstrate that no interaction occurs between the two antibodies. Table 4-2 provides the composition of the three products.

Table 4-2: Study Drug Composition for CA209742

Component	Nivolumab	Ipilimumab	Fixed Ratio Combination
Nivolumab	10 mg/mL		1.54 mg/mL
Ipilimumab		5 mg/mL	4.62 mg/mL
Sodium Citrate	20 mM		1.54 mM
Tris Hydrochloride		20 mM	18.46 mM
Sodium Chloride	50 mM	100 mM	96.15 mM
Mannitol	3%	1%	1.15%
Pentetic Acid	20 µM	100 µM	93.85 µM
Polysorbate 80	0.02% w/v	0.01% w/v	0.012% w/v

4.1 Investigational Product

An investigational product, also known as investigational medicinal product in some regions, is defined a pharmaceutical form of an active substance or placebo being tested or used as a reference in a clinical study, including products already with a marketing authorization but used or assembled (formulated or packaged) differently than the authorized form, or used for an unauthorized indication, or when used to gain further information about the authorized form.

The investigational product should be stored in a secure area according to local regulations. It is the responsibility of the investigator to ensure that investigational product is only dispensed to study subjects. The investigational product must be dispensed only from official study sites by authorized personnel according to local regulations. In this protocol, investigational products are:

- Nivolumab
- Ipilimumab
- BMS-986214 (Nivolumab/Ipilimumab 1:3)

4.2 Non-investigational Product

Other medications used as support or escape medication for preventative, diagnostic, or therapeutic reasons, as components of the standard of care for a given diagnosis, may be considered as non-investigational products.

4.3 Storage of Study Drug

The product storage manager should ensure that the study drug is stored in accordance with the environmental conditions (temperature, light, and humidity) as determined by BMS. If concerns regarding the quality or appearance of the study drug arise, the study drug should not be dispensed and contact BMS immediately.

Study drug not supplied by BMS will be stored in accordance with the package insert.

Please refer to [Section 9.2.2](#) for guidance on IP records and documentation.

4.3.1 Part 1 Study Drug Administration

In Part 1 of the study there will be two treatment arms:

Arm A BMS-986214 will be administered as one 60 minute infusion on Day 1 of each treatment cycle every 3 weeks for 4 doses or until progression, unacceptable toxicity, withdrawal of consent, or the study ends, whichever occurs first.

Arm B nivolumab and ipilimumab will be administered sequentially, as two separate infusions, one 60 minute nivolumab infusion and one 90 minute ipilimumab infusion with a 30 minute break between each infusion. Nivolumab is to be administered first. Subjects should receive nivolumab at a dose of 1 mg/kg (Arm B) as a 60-minute IV infusion, on Day 1 of each treatment cycle every 3 weeks for 4 doses or until progression, unacceptable toxicity, withdrawal of consent, or the study ends, whichever occurs first.

The nivolumab infusion must be promptly followed by a saline flush to clear the line of nivolumab before starting the next infusion.

The second infusion will always be ipilimumab, and the time in between infusions is expected to be approximately 30 minutes but may be more or less depending on the situation. Subjects should receive ipilimumab at a dose of 3 mg/kg as a 90-minute IV infusion, on Day 1 of each treatment cycle every 3 weeks for 4 doses or until progression, unacceptable toxicity, withdrawal of consent, or the study ends, whichever occurs first.

The risk/benefit profile for nivolumab has primarily been investigated using a 60-minute infusion and for ipilimumab a 90-minute infusion. Previous clinical studies of nivolumab have used 60-minute infusion duration and for ipilimumab 90-minute. Both nivolumab and ipilimumab have been administered safely at doses ranging up to 10 mg/kg over these infusion durations. Overall, infusion reactions including high-grade hypersensitivity reactions have been uncommon across multiple clinical studies, and all have been managed by following the safety algorithms.

Both agents given as single agent is uncommonly associated with infusion reactions, incidence less than 1% for ipilimumab (Yervoy® FDA Label) and for nivolumab 3%.¹⁴ In the CA209069 study, hypersensitivity/infusion reactions were listed as 3.2% for the combination and 2.2% for ipilimumab. No Grade 3 or Grade 4 hypersensitivity/infusion reactions were observed in either the combination or single agent ipilimumab treatment groups.³²

Subjects should be carefully monitored for infusion reactions during study drug administration. If an acute infusion reaction is noted, subjects should be managed according to [Section 4.5.6](#).

The **pharmacy manual** includes detailed instructions for study medication preparation.

Dosing calculations should be based on the body weight assessed at screening. It is not necessary to re-calculate subsequent doses if the subject weight is within 10% of the weight used to calculate the previous dose. All doses should be rounded to the nearest milligram.

During Part 1, subjects may be dosed no less than 19 days between doses. If dosing is delayed, both nivolumab and ipilimumab must be delayed together. If dosing is resumed after a delay, both nivolumab and ipilimumab must be resumed on the same day.

Detailed instructions for dilution and infusion of study drug injection may be provided in the pharmacy binder, pharmacy reference sheet or current investigator brochures.^{31,33} Care must be taken to assure sterility of the prepared solution as the product does not contain any antimicrobial preservative or bacteriostatic agent.

4.3.2 Part 2 Study Drug Administration

Starting 6 weeks after the last co-administered dose in Part 1, subjects will be administered a flat dose 480 mg nivolumab 30 minute infusion every 4 weeks (Q4W) until unacceptable toxicity or disease progression (total maximum treatment duration up to 2 years including Part 1 and Part 2).

Subjects may be dosed up to 3 days after the scheduled date if necessary. Subsequent dosing should be based on the actual date of administration of the previous dose of drug. Every effort should be made to adhere to protocol treatment schedule of administration of nivolumab every 4 weeks in the maintenance phase. In extenuating circumstances in which the patient cannot make the dosing schedule within the 3-day window, BMS Monitor should be contacted.

For details on prepared drug storage, preparation, and administration, please refer to the nivolumab, ipilimumab and BMS-986214 IBs and/or pharmacy reference sheets.

4.4 Method of Assigning Subject Identification

CA209742 is a randomized study. After the subject's initial eligibility is established and informed consent has been obtained, the subject must be enrolled into the study by accessing an Interactive Response Technologies web-based system (IRT) to obtain the subject number. Every subject that signs the informed consent form must be assigned a subject number in IRT. Specific instructions for using IRT will be provided to the investigational site in a separate document. The investigator or designee will register the subject for enrollment by following the enrollment procedures established by BMS. The following information is required for enrollment:

- Date that informed consent was obtained
- Date of birth
- Gender at birth.

Once enrolled in IRT, enrolled subjects that have met all eligibility criteria will be ready to be randomized through the IRT. The following information is required for subject randomization:

- Subject number
- Date of birth
- PD-L1 expression level (PD-L1 \geq 5% expression vs PD-L1 $<$ 5% expression/indeterminate) entered by vendor
- M Stage at screening (M0/M1a/M1b vs. M1c) (See [Appendix 4](#)).

Subjects meeting all eligibility criteria will randomize 1:1 ratio to Arm A or Arm B and stratified by the following factors:

- PD-L1 expression
- M stage.

The randomization procedures will be carried out via permuted blocks within each stratum. The exact procedures for using the IRT will be detailed in the IRT manual.

Nivolumab injection is to be administered as an IV infusion through a 0.2-micron to 1.2-micron pore size, low-protein binding (polyethersulfone membrane) in-line filter at the protocol specified doses and infusion times. It is not to be administered as an IV push or bolus injection. Nivolumab injection can be infused undiluted (10 mg/mL) or diluted with 0.9% Sodium Chloride Injection, USP or 5% Dextrose Injection, USP to protein concentrations as low as 0.35 mg/mL. During drug product preparation and handling, vigorous mixing or shaking is to be avoided. Instructions for dilution and infusion of nivolumab injection may be provided in the clinical protocol, pharmacy binder, pharmacy manual, or pharmacy reference sheet. Care must be taken to assure sterility of the prepared solution as the product does not contain any antimicrobial preservative or bacteriostatic agent. Nivolumab infusions are compatible with polyvinyl chloride (PVC) or polyolefin containers and infusion sets, and glass bottles. Vials of nivolumab injection must be stored at 2°C to 8°C (36°F to 46°F) and protected from light and freezing.

Ipilimumab injection can be used for IV administration without dilution after transferring to a PVC, non-PVC/non-DEHP or glass container and is stable for 24 hours at 2-8°C or room temperature/room light (RT/RL). For ipilimumab storage instructions, refer to ipilimumab IB and/or pharmacy reference sheets.

Separate infusion bags and filters should be used when administering nivolumab and ipilimumab on the same day.

Ipilimumab is to be administered as a ~90 minute IV infusion, using a volumetric pump with a 0.2 to 1.2 micron in-line filter at the protocol-specified dose. The drug can be diluted with 0.9% normal saline or 5% Dextrose Injection to concentrations between 1 mg/mL and 4 mg/mL. It is not to be administered as an IV push or bolus injections. Care must be taken to assure sterility of the prepared solutions, since the drug product does not contain any antimicrobial preservatives or bacteriostatic agents. At the end of the infusion, flush the line with a sufficient quantity of normal saline or 5% dextrose solution.

BMS-986214 injection is to be administered as an IV infusion through a 0.2-micron pore size, low-protein binding in-line filter at the protocol-specified doses and infusion times. It is not to be administered as an IV push or bolus injection. Prior to infusion, the BMS-986214 injection is diluted with 0.9% Sodium Chloride Injection, United States Pharmacopeia (USP) to required concentrations.

BMS-986214 is available as a solution at a concentration of 6.2 mg/ml. The volume for calculated weight based dose (refer to pharmacy reference sheets) is to be added to 40 ml of 0.9% Sodium Chloride (normal saline) USP prior to being administered to the patient as an infusion, at a flow rate of less than or equal to 2.5 ml/min over ~60 minutes.

During drug product preparation and handling, vigorous mixing or shaking is to be avoided. Vials of BMS-986214 injection must be stored at 2° to 8°C (36° to 46°F) protected from light and it must not be frozen. Further instructions for dilution and infusion of BMS-986214 injection may be provided in the clinical protocol, pharmacy binder, or pharmacy reference sheet. Care must be taken to assure sterility of the prepared solution as the product does not contain any antimicrobial preservative or bacteriostatic agent. No incompatibilities between BMS-986214 and polyvinyl chloride (PVC) and polyolefin containers/IV components have been observed.

4.5.1 Dose Delay Criteria

Regardless of whether or not the event is attributed to nivolumab, ipilimumab, or BMS-986214, all study drugs must be delayed until treatment can resume. Tumor assessments for all subjects should continue as per protocol even if dosing is delayed. During Part 1, both nivolumab and ipilimumab should be discontinued at the same time.

Nivolumab, ipilimumab, and BMS-986214 administration should be delayed for the following:

- Any Grade \geq 2 non-skin, drug-related adverse event, with the following exception:
 - Grade 2 drug-related fatigue does not require a treatment delay
 - Grade 2 drug-related creatinine, AST, ALT or Total Bilirubin abnormalities
- Any Grade 3 skin, drug-related adverse event
- Any Grade 3 drug-related laboratory abnormality (excluding AST, ALT or Total Bilirubin), with the following exceptions for lymphopenia, and asymptomatic amylase or lipase:
 - Grade 3 lymphopenia does not require dose delay
 - Any Grade \geq 3 drug-related amylase or lipase abnormality that is not associated with symptoms or clinical manifestations of pancreatitis does not require dose delay
- Any adverse event, laboratory abnormality, or intercurrent illness which, in the judgment of the investigator, warrants delaying the dose of study medication

Subjects who require delay of study drug should be re-evaluated weekly or more frequently if clinically indicated and resume dosing when re-treatment criteria are met.

4.5.2 Criteria to Resume Treatment

Subjects may resume treatment with study drug when the drug-related AE(s) resolve to Grade ≤ 1 or baseline value, with the following exceptions:

- Subjects may resume treatment in the presence of Grade 2 fatigue
- Subjects who have not experienced a Grade 3 drug-related skin AE may resume treatment in the presence of Grade 2 skin toxicity
- For subjects with Grade 2 AST, ALT, or TBIL elevation, dosing may resume when laboratory values return to baseline and management with corticosteroids, if needed, is complete
- Subjects with combined Grade 2 AST/ALT AND total bilirubin values meeting discontinuation parameters (Section 4.5.2) should have treatment permanently discontinued
- Drug-related pulmonary toxicity, diarrhea or colitis must have resolved to baseline before treatment is resumed. Subjects with persistent Grade 1 pneumonitis after completion of a steroid taper over at least 1 month may be eligible for retreatment if discussed with and approved by BMS Medical Monitor

Subjects with drug-related endocrinopathies adequately controlled with only physiologic hormone replacement may resume treatment after consultation with the BMS Medical Monitor.

4.5.3 Dose Discontinuation

Any Grade 3 non-skin, drug-related adverse event lasting > 7 days, or recurs with the following exceptions for laboratory abnormalities, diarrhea drug-related uveitis, pneumonitis, bronchospasm, hypersensitivity reactions, infusion reactions, and endocrinopathies:

- Grade 3 drug-related diarrhea, uveitis, pneumonitis, bronchospasm, hypersensitivity reaction, or infusion reaction of any duration requires discontinuation
- Grade 3 drug-related endocrinopathies adequately controlled with only physiologic hormone replacement do not require discontinuation
- Grade 3 drug-related laboratory abnormalities do not require treatment discontinuation except:
 - Grade 3 drug-related thrombocytopenia > 7 days or associated with bleeding requires discontinuation
 - Any drug-related liver function test (LFT) abnormality that meets the following criteria require discontinuation:
 - Grade ≥ 3 drug-related AST, ALT or Total Bilirubin requires discontinuation*
 - Concurrent AST or ALT $> 3 \times$ ULN and total bilirubin $> 2 \times$ ULN

* In most cases of Grade 3 AST or ALT elevation, study drug(s) will be permanently discontinued. If the investigator determines a possible favorable benefit/risk ratio that warrants continuation of study drug(s), a discussion between the investigator and the BMS Medical Monitor/designee must occur.

- Any Grade 4 drug-related adverse event or laboratory abnormality (including but not limited to creatinine, AST, ALT, or Total Bilirubin), except for the following events which do not require discontinuation:
 - Grade 4 neutropenia \leq 7 days
 - Grade 4 lymphopenia or leukopenia
 - Isolated Grade 4 amylase or lipase abnormalities that are not associated with symptoms or clinical manifestations of pancreatitis
 - Isolated Grade 4 electrolyte imbalances/abnormalities that are not associated with clinical sequelae and are corrected with supplementation/appropriate management within 72 hours of their onset
 - Grade 4 drug-related endocrinopathy adverse events, such as adrenal insufficiency, ACTH deficiency, hyper- or hypothyroidism, or glucose intolerance, which resolve or are adequately controlled with physiologic hormone replacement (corticosteroids, thyroid hormones) or glucose-controlling agents, respectively, may not require discontinuation after discussion with and approval from the BMS Medical Monitor
- Any event that leads to delay in dosing lasting $>$ 6 weeks from the previous dose requires discontinuation, with the following exceptions:
 - Dosing delays to allow for prolonged steroid tapers to manage drug-related adverse events are allowed. Prior to re-initiating treatment in a subject with a dosing delay lasting $>$ 6 weeks from the previous dose, the BMS medical monitor must be consulted. Tumor assessments should continue as per protocol even if dosing is delayed. Periodic study visits to assess safety and laboratory studies should also continue every 6 weeks or more frequently if clinically indicated during such dosing delays.
 - Dosing delays lasting $>$ 6 weeks from the previous dose that occur for non-drug-related reasons may be allowed if approved by the BMS medical monitor. Prior to re-initiating treatment in a subject with a dosing delay lasting $>$ 6 weeks, the BMS medical monitor must be consulted. Tumor assessments should continue as per protocol even if dosing is delayed. Periodic study visits to assess safety and laboratory studies should also continue every 6 weeks or more frequently if clinically indicated during such dosing delays

Any adverse event, laboratory abnormality, or intercurrent illness which, in the judgment of the Investigator, presents a substantial clinical risk to the subject with continued nivolumab dosing.

4.5.4 Treatment Beyond Disease Progression

Accumulating evidence indicates a minority of subjects treated with immunotherapy may derive clinical benefit despite initial evidence of PD.⁷

Subjects treated with study drug(s) will be permitted to continue treatment beyond initial RECIST 1.1 defined PD in both Part 1 and Part 2, assessed by the investigator, as long as they meet the following criteria:

- Investigator-assessed clinical benefit
- Tolerance of study drug

- Stable performance status
- Treatment beyond progression will not delay an imminent intervention to prevent serious complications of disease progression (eg, CNS metastases)
- Subject provides written informed consent prior to receiving additional nivolumab treatment. All other elements of the main consent including description of reasonably foreseeable risks or discomforts, or other alternative treatment options will still apply

A radiographic assessment/ scan should be performed within 6 weeks of initial investigator-assessed progression to determine whether there has been a decrease in the tumor size or continued PD. The assessment of clinical benefit should be balanced by clinical judgment as to whether the subject is clinically deteriorating and unlikely to receive any benefit from continued treatment with nivolumab.

If the investigator feels that the subject continues to achieve clinical benefit by continuing treatment, the subject should remain on the trial and continue to receive monitoring according to the Time and Events Schedule.

For the subjects who continue study therapy beyond progression, further progression is defined as an additional 10% increase in tumor burden with a minimum 5 mm absolute increase from time of initial PD. This includes an increase in the sum of diameters of all target lesions and/ or the diameters of new measurable lesions compared to the time of initial PD. Nivolumab treatment should be discontinued permanently upon documentation of further progression.

New lesions are considered measurable at the time of initial progression if the longest diameter is at least 10 mm (except for pathological lymph nodes which must have a short axis of at least 15 mm). Any new lesion considered non-measurable at the time of initial progression may become measurable and therefore included in the tumor burden if the longest diameter increases to at least 10 mm (except for pathological lymph nodes which must have a short axis of at least 15 mm). In situations where the relative increase in total tumor burden by 10% is solely due to inclusion of new lesions which become measurable, these new lesions must demonstrate an absolute increase of at least 5 mm.

4.5.5 *Management Algorithms for Immuno-Oncology Agents*

Immuno-oncology (I-O) agents are associated with AEs that can differ in severity and duration than AEs caused by other therapeutic classes. Nivolumab, ipilimumab, and BMS-986214 are considered immuno-oncology agents in this protocol. Early recognition and management of AEs associated with immuno-oncology agents may mitigate severe toxicity. Management Algorithms have been developed to assist investigators in assessing and managing the following groups of AEs:

- Gastrointestinal
- Renal
- Pulmonary
- Hepatic

- Endocrinopathy
- Skin
- Neurological

The above algorithms are found in the [Appendix 3](#) of this protocol.

4.5.6 Treatment of Related Infusion Reactions

Since study drug contains only human immunoglobulin protein sequences, it is unlikely to be immunogenic and induce infusion or hypersensitivity reactions. However, if such a reaction were to occur, it might manifest with fever, chills, rigors, headache, rash, pruritus, arthralgias, hypotension, hypertension, bronchospasm, or other allergic-like reactions. All Grade 3 or 4 infusion reactions should be reported within 24 hours to the study medical monitor and reported as an SAE if it meets the criteria. Infusion reactions should be graded according to NCI CTCAE (Version 4.0) guidelines.

Treatment recommendations are provided below and may be modified based on local treatment standards and guidelines, as appropriate:

For Grade 1 symptoms: (mild reaction; infusion interruption not indicated; intervention not indicated):

- Remain at bedside and monitor subject until recovery from symptoms. The following prophylactic premedications are recommended for future infusions: diphenhydramine 50 mg (or equivalent) and/or acetaminophen/paracetamol 325 to 1000 mg at least 30 minutes before additional nivolumab administrations

For Grade 2 symptoms: (moderate reaction required therapy or infusion interruption but responds promptly to symptomatic treatment (eg, antihistamines, non-steroidal anti-inflammatory drugs, narcotics, corticosteroids, bronchodilators, IV fluids); prophylactic medications indicated for ≤ 24 hours):

- Stop the study drug infusion, begin an IV infusion of normal saline, and treat the subject with diphenhydramine 50 mg IV (or equivalent) and/or acetaminophen/paracetamol 325 to 1000 mg; remain at bedside and monitor subject until resolution of symptoms. Corticosteroid and/or bronchodilator therapy may also be administered as appropriate. If the infusion is interrupted, then restart the infusion at 50% of the original infusion rate when symptoms resolve; if no further complications ensue after 30 minutes, the rate may be increased to 100% of the original infusion rate. Monitor subject closely. If symptoms recur, then no further study drug will be administered at that visit
- For future infusions, the following prophylactic premedications are recommended: diphenhydramine 50 mg (or equivalent) and/or acetaminophen/paracetamol 325 to 1000 mg should be administered at least 30 minutes before nivolumab infusions. If necessary, corticosteroids (up to 25 mg of hydrocortisone or equivalent) may be used

For Grade 3 or 4 symptoms: (severe reaction, Grade 3: prolonged [ie, not rapidly responsive to symptomatic medication and/or brief interruption of infusion]; recurrence of symptoms following initial improvement; hospitalization indicated for other clinical sequelae (eg, renal impairment, pulmonary infiltrates). Grade 4: Life-threatening; pressor or ventilatory support indicated):

- Immediately discontinue infusion of study drug. Begin an IV infusion of normal saline and treat the subject as follows: Recommend bronchodilators, epinephrine 0.2 to 1 mg of a 1:1000 solution for subcutaneous administration or 0.1 to 0.25 mg of a 1:10,000 solution injected slowly for IV administration, and/or diphenhydramine 50 mg IV with methylprednisolone 100 mg IV (or equivalent), as needed. Subject should be monitored until the Investigator is comfortable that the symptoms will not recur. Study drug will be permanently discontinued. Investigators should follow their institutional guidelines for the treatment of anaphylaxis. Remain at bedside and monitor subject until recovery of the symptoms

In case of late-occurring hypersensitivity symptoms (eg, appearance of a localized or generalized pruritus within 1 week after treatment), symptomatic treatment may be given (eg, oral antihistamine or corticosteroids).

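### The Grade 2 advice in Protocol 4.5.6 for symptoms that recur after restart points away from the permanent stop that the protocol as a whole requires

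*Protocol*

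**What the plan says.** Section 4.5.6 of the protocol sets out management of infusion reactions by grade.

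- **Grade 2, first bullet.** Stop the infusion and treat. If the infusion was interrupted, "then restart the infusion at 50% of the original infusion rate when symptoms resolve". Then: "If symptoms recur, then no further study drug will be administered at that visit".
- **Grade 2, second bullet.** "For future infusions, the following prophylactic premedications are recommended". It makes no exception for a subject whose symptoms came back after restart.
- **Grade 3 or 4.** The printed Grade 3 description includes "recurrence of symptoms following initial improvement". The action is "Study drug will be permanently discontinued".

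Section 4.5.3 states the stopping rule separately. For Grade 3 drug-related events, a "hypersensitivity reaction, or infusion reaction of any duration requires discontinuation". Section 4.5.2 governs what happens when the event stays below that threshold: "Subjects may resume treatment with study drug when the drug-related AE(s) resolve to Grade" 1 or less, or to baseline.

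Two other statements in 4.5.6 bear on the reading. Infusion reactions are to be graded by CTCAE version 4.0, and the treatment advice is labelled as recommendations that sites may adapt to local standards. Reporting depends on the grade: "All Grade 3 or 4 infusion reactions should be reported within 24 hours to the study medical monitor".

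**The concern.** The same clinical event, a recurrence after an interrupted infusion has been restarted, has two printed actions a few lines apart. The Grade 2 bullet withholds drug for the visit and moves on to preparing for the next infusion. The Grade 3 paragraph ends treatment. The Grade 2 bullet does not tell the site to regrade and does not point to 4.5.3.

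If a site leaves the event at Grade 2, three things could follow:

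1. The subject could be re-dosed under 4.5.2 after a reaction for which the protocol requires a permanent stop.
2. The 24-hour report to the medical monitor, which is triggered by Grade 3 or 4, could be missed.
3. The event could drop out of the drug-related and all-causality Grade 3-5 AE rates (Protocol 8.3.2; SAP 4.2.3 and 4.2.4).

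The setting gives the wording some weight. The trial's primary question is about reactions around the infusion of a new fixed-ratio product. Sections 4.3.1 and 4.5 send sites to 4.5.6 for acute reactions, infusion reactions are not among the algorithm groups listed in 4.5.5, and there is no data monitoring committee (Section 7).

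**Working it through.** **Reading the passages together**

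1. Restart is allowed only after symptoms have resolved (4.5.6, Grade 2). Any recurrence after restart therefore follows an initial improvement.
2. Recurrence after initial improvement is an element of the printed Grade 3 description (4.5.6, Grade 3 or 4). The event meets that description.
3. Grade 3 leads to permanent discontinuation in 4.5.6 and, for drug-related reactions, in 4.5.3.
4. The Grade 2 bullet limits its instruction to the current visit. That limit has little purpose if every recurrence ends treatment, and the bullet after it looks ahead to further infusions. The wording therefore points the other way, and this is more than a missing cross-reference.
5. If the event is left at Grade 2, 4.5.1 calls for a delay for Grade 2 or higher non-skin drug-related events. Under 4.5.2 the delay ends at Grade 1 or less, which an acute reaction may reach before the next 3-weekly dose.

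**Size**

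The plan gives no figure for this event, so there is none to reproduce. Inputs:

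- Hypersensitivity/infusion reactions with the combination in CA209069: 3.2%, none Grade 3 or 4 (Protocol 4.3.1). That study did not use the fixed-ratio product, so the rate may not carry over to Arm A.
- Treated subjects: 100, or 50 per arm (Protocol 8.1).
- Share of reactions that are interrupted, restarted and then recur: not in the documents. Assumed 5% to 25%.

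Expected reactions of any grade: 0.032 × 100 = 3.2 in the trial; 0.032 × 50 = 1.6 per arm.

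Expected recurrences after restart per 100 subjects: 3.2 × 0.05 = 0.16; 3.2 × 0.25 = 0.8.

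Chance of at least one in 100 subjects:

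- low: 1 − (1 − 0.0016)^100 = 14.8%
- high: 1 − (1 − 0.008)^100 = 55.2%

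Effect of one undergraded event on a Grade 3-5 AE rate: at most 1/50 = 2.0 percentage points in that arm, and 0 if the subject has another Grade 3-5 event that counts towards the same rate.

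Effect of grading on the primary, narrow-SMQ and select-AE incidence rates: 0, because they count subjects with a qualifying event of any grade. Only their worst-grade tables could shift.

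**The case against.** The strongest reply is that the text can be reconciled. Section 4.5.6 itself requires CTCAE version 4.0 grading, the Grade 3 description is in the very next paragraph, and withholding drug for the visit is a bedside step that does not rule out stopping for good. The Grade 2 bullet is advisory, while 4.5.3 carries no such label and would prevail. This stands. A reader might infer that the protocol authorises re-dosing after a Grade 3 reaction; taken as a whole, it does not.

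Other safeguards also exist. A serious recurrence must be reported within 24 hours whatever its grade, and an SAE report is needed where seriousness is in doubt (6.1.1). The investigator may stop treatment on judgment (3.5 and the end of 4.5.3), and the medical monitor reviews adverse events continuously (3.1). These confine the reporting gap mainly to non-serious recurrences and lower the chance of re-dosing. They do not change what the Grade 2 bullet tells the site to do at the moment of recurrence, and several of them depend on judgment or on later review.

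A third objection concerns the 15% to 55%. That range is the chance that a recurrence occurs. Harm would also need the site to undergrade it, review to miss it, and the subject to be re-dosed. This is correct, and no probability for those steps is available from the documents.

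**Conclusion.** The point holds as a wording problem with a safety consequence, and it should be corrected. The protocol as a whole requires regrading to Grade 3 and a permanent stop, but the Grade 2 bullet, followed literally, could lead a site to leave the event at Grade 2 and re-dose.

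It is expected to be rare. The 15% to 55% rests on a rate from a study without the fixed-ratio product and on an assumed recurrence share. Given those inputs, it is an upper bound on the chance of harm in the trial. The effect on a Grade 3-5 AE rate is at most 2.0 percentage points per event in an arm of 50.

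A reader might infer that the primary comparison is biased. The documents do not support that: grade plays no part in whether a subject counts towards the primary, narrow-SMQ or select-AE rates. The zero covers grading only. Re-dosing could in principle lead to a later qualifying event, and nothing in the documents allows that to be sized.

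**What to change.** Replace the recurrence sentence in the Grade 2 bullet with wording to this effect: *If symptoms recur after restart, stop the infusion. Recurrence after initial improvement meets the Grade 3 definition below and is to be graded, reported and managed as Grade 3, with permanent discontinuation per 4.5.3.* Limit the premedication bullet that follows to subjects without recurrence.

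No added patients, procedures or CRF fields are needed. Interruptions and rate reductions are already documented (Protocol 5.3) and summarised with reasons (SAP 7.4.2.2).

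The real cost is clinical. A subject with only mild recurrent symptoms permanently loses study therapy, and in Part 1 both antibodies stop together (3.1.2). The existing Grade 3 rule already requires this, so the change adds no new stopping criterion. If the sponsor means some recurrences to stay at Grade 2, the Grade 3 description in 4.5.6 needs an explicit exception instead, made consistent with 4.5.3.
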